Individuals diagnosed with melanoma are at increased risk for second primary melanoma and disease recurrence, and it is recommended that they periodically receive a total cutaneous examination (TCE) from a physician, perform a regular SSE, and routinely engage in sun protection behaviors (NCCN, 2011). Although patients typically have a periodic TCE, our previous research suggests that more than two-thirds of them do not perform a thorough, full-body SSE on a sufficiently regular basis (Manne & Lessin, 2006). We have also found that many patients fail to engage in one or more sun protection behaviors (Coups & Ostroff, 2005). There is a critical need to develop effective interventions to promote SSE and sun protection behaviors among melanoma patients. In this research, we will develop and test an innovative web-based intervention to promote skin surveillance and sun protection behaviors among melanoma patients.

Protocol Version Date: 4/5/22

The project will be conducted in three phases. Phase 1 focuses on intervention development, usability testing, and refinement. In Phase 2, we will conduct a randomized controlled trial (RCT) comparing the efficacy of an interactive tailored website (ITW) versus Usual Care in promoting SSE and sun protection behaviors among melanoma patients who completed surgical treatment from 3–24 months previously. In Phase 3, we will conduct qualitative interviews in order to obtain feedback on the ITW.

Aim 1 (primary aim): To evaluate the impact of the ITW versus Usual Care on SSE and sun protection behaviors among individuals diagnosed with melanoma. Hypothesis. Individuals assigned to the ITW will be more likely to engage in SSE and sun protection behaviors than those assigned to Usual Care.

Aim 2 (secondary aim): To examine mediators of the impact of the intervention. Hypothesis. The effects of the intervention on SSE and sun protection behaviors will be mediated by melanoma knowledge, self-efficacy for SSE and sun protection behaviors, perceived benefits of SSE and sun protection behaviors, perceived barriers to SSE and sun protection behaviors, and perceived controllability of melanoma.

Aim 3 (exploratory aim): To examine moderators of the impact of the intervention. Research Question. To evaluate whether ITW effects are moderated by the following factors: time since diagnosis, disease stage, age, sex, income, education, Internet experience, distress about melanoma, worry about recurrence, and evaluation and usage of the ITW.

2. Background and Significance

2.1. Melanoma Incidence, Recurrence, Second Primaries, and Survival

Currently, more than 920,000 individuals in the U.S. are living with a personal history of melanoma (Howlader et al., 2013). Unlike the vast majority of cancers, the incidence of melanoma has increased over the past several decades (e.g., 2.8% increase per year since 1992), which is only partly attributable to improvements in disease detection and reporting (Linos et al., 2009). In 1960, the lifetime risk of melanoma in the U.S. was 1 in 800 (Lens & Dawes, 2004) and it is currently 1 in 37 for men and 1 in 55 for women (American Cancer Society, 2011). Melanoma incidence rates have increased most notably among men over the age of 65 years (Erickson & Driscoll, 2010). The incidence of melanoma is highest among non-Hispanic white individuals and those with a higher socioeconomic status (Little & Eide, 2012; Russak & Rigel, 2012; Singh et al., 2011).

Individuals diagnosed with melanoma remain at risk for disease recurrence, second primary melanomas, and non-melanoma skin cancer. Among individuals diagnosed with localized or regional stage disease, estimated rates of recurrence for thin melanomas vary from 3-24%, with recurrence rates for thicker melanomas or tumors with lymph node involvement being substantially higher (e.g., 51% among those with stage III disease) (Francken et al., 2005; Francken et al., 2008; Leiter et al., 2012). An estimated 4-11% of melanoma patients will be diagnosed with one or more second primary melanomas (Bradford et al., 2010; Freedman et al., 2006; Ferrone et al., 2005). Recurrent or new primary melanomas occur most commonly during the first five years after diagnosis, but can also arise many years later (Christianson & Anderson, 2003; NCCN, 2011). Recurrent melanoma is highly amenable to early detection by patients or via clinical examination. Most melanoma patients receive a periodic TCE from a physician (Barzilia et al., 2004; Coups et al., 2010; Federman et al., 2004; Federman et al., 2006), but do not engage in regular SSE (Manne & Lessin, 2006; Loescher et al., 2006; Mujumdar et al., 2009). More than half of all recurrences and new primary melanomas are detected by patients themselves (Francken et al., 2007; Moore Dalal et al., 2008), which provides optimism that promoting patients' engagement in SSE will further enhance early detection of recurrences and new primaries. Detection and treatment of recurrent disease and new primary melanomas at earlier stages leads to improved survival (Leiter et al., 2010).

Protocol Version Date: 4/5/22

2.2. Skin Surveillance and Sun Protection Behaviors among Individuals with Melanoma

Follow-up guidelines for melanoma recommend that patients receive a periodic TCE from a physician and conduct a monthly thorough SSE (NCCN, 2011), which entails a deliberate, systematic inspection of all areas of the body, using a mirror or the assistance of another person to examine hard to view areas (Weinstock et al., 2004). It is also recommended that patients engage in a variety of sun protection behaviors that limit their exposure to ultraviolet (UV) light (NCCN, 2011), such as wearing clothing that covers or shades exposed skin, using sunscreen with a sun protection factor (SPF) of 30 or higher, and seeking shade when outside on a sunny day.

Although most patients receive a periodic physician TCE (Barzilia et al., 2004; Coups et al., 2010; Federman et al., 2004; Federman et al., 2006), the majority do not perform a regular, thorough SSE and do not sufficiently engage in recommend sun protection behaviors (Manne & Lessin, 2006; Loescher et al., 2006; Mujumdar et al., 2009). Only 12-33% of melanoma patients report performing a thorough SSE at least every two months (Bowen et al., 2012; Loescher et al., 2006; Mujumdar et al., 2009). Manne and Lessin (2006) found that 39% of melanoma patients reported conducting a SSE every month, but only 14% of them conducted a thorough examination. In a recent needs assessment survey, we found that 72% of melanoma patients reported doing a SSE in the past 2 months, but only 12% performed a thorough examination (defined as examining all body parts at least once). Performing a thorough SSE is important because it has been shown to lead to the detection of thinner, early stage melanomas (Pollitt et al., 2009) and is associated with longer disease survival (Moore Dalal et al., 2008). In one study, 23% of melanoma patients met criteria for engaging in regular sun protection behaviors (Mujumdar et al., 2009). Coups and Ostroff (2005) found that 10% of melanoma patients reported always engaging in each of four sun protection behaviors (wearing a hat, wearing a long-sleeved shirt, using sunscreen, and staying in the shade). These studies demonstrate the need to develop and disseminate effective interventions to promote skin surveillance and sun protection behaviors among melanoma patients.

2.3. Web-Based Health Behavior Interventions

There is considerable evidence that the Internet can be used to deliver tailored (i.e., personalized) interventions that promote changes in various health behaviors across diverse groups, including medical populations (Bennett & Glasgow, 2009; Portnoy et al., 2007; Webb & Sheeran, 2006). Compared to other delivery channels (such as in person, telephone, print, or mass media), the Internet provides an ideal channel for delivering tailored health behavior interventions, as it has the capability to manage the key elements needed for tailored communications: collecting each individual's unique attitudes, beliefs, and behaviors; storing a database of tailored messages; storing and applying a set of algorithms to guide the tailoring; and delivering the tailored information to each individual (Kreuter et al., 2000). Additional advantages of delivering health behavior interventions via the Internet as opposed to other channels include: high convenience for patients; ability to use highly interactive content and engaging multi-media materials; ease of updating intervention content; cost-effectiveness, particularly with regard to the marginal costs of providing the intervention to additional patients; high treatment fidelity; ability to reach patients across geographical locations; and high potential for widespread adoption and dissemination of efficacious interventions (Bennett & Glasgow, 2009).

2.4. Internet Penetration and Health Information Seeking

Currently, 85% of adults in the U.S. report using the Internet (Pew Internet & American Life Project), as do 88% of adults in New Jersey (Internet World Stats). While Internet use is almost ubiquitous among young adults (98% of 18–29 year olds), an increasing number of older adults are also using the Internet (83% of 50–64 year olds and 56% of those \geq 65 years) (Pew Internet & American Life Project). More than

Protocol Version Date: 4/5/22

80% of Internet users have high-speed broadband connection at home. With the aging of the baby boomer generation, it is expected that older adults will continue to be one of the fastest growing groups of Internet users.

The Internet is an increasing source of health information for healthy adults as well as patients with a variety of medical conditions. Among Internet users, 83% report having looked online for health information (Pew Internet & American Life Project). More than two-thirds of individuals diagnosed with cancer report looking for cancer information and the most common source of information is the Internet (Mayer et al., 2007). Relatively little research has examined Internet use among melanoma patients. A study conducted from 2001-2003 of 1,613 melanoma patients treated at a single institution found that 39% had researched their disease on the Internet, 94% of whom found the Internet to provide useful information (Sabel et al., 2005). Rates of Internet usage have increased considerably since 2003, particularly among older adults. A recent study of 55 melanoma patients found that 84% used the Internet at least on a weekly basis (Marble et al., 2010). Almost three-quarters (73%) preferred to receive melanoma health education via computerbased as opposed to other types of technology (e.g., DVD, MP3, videotape). In our own recent survey of 176 melanoma patients at Rutgers Cancer Institute of New Jersey (Rutgers CINJ), 84% reported using the Internet. Among the Internet users, 78% reported ever looking for information about melanoma on the Internet and 93% had ever looked for information about any health topic. In sum, the increasing penetration of the Internet, particularly among older adults, and the fact that many melanoma patients have Internet access and seek information online, suggest that a web-based intervention is a viable approach for promoting health behavior change among these patients.

3. Research Design and Methods

In this project, we will develop and test a web-based intervention to promote SSE and sun protection behaviors among melanoma patients. The project will be conducted in two phases: Phase 1 – intervention development, usability testing, and refinement; Phase 2 – RCT of the efficacy of an ITW versus Usual Care in promoting SSE and sun protection behaviors. Phase 3 – obtain feedback on the acceptability and usability of the ITW through phone interviews with study participants who have completed the intervention.

3.1. Phase 1: Intervention Development, Usability Testing, and Refinement

During this phase, we will develop, test, and finalize the ITW to be used in the RCT to be conducted in Phase 2. Our overall approach to the design, content, and features of the website will be guided by best practices in health communications and website design (Centers for Disease Control and Prevention, 2009; National Institutes of Health, 2008; U.S. Department of Health and Human Services, 2006) and by Ritterband and colleagues' (2009) Internet Intervention Model, which offers guidelines regarding website characteristics and features that improve users' experience and facilitate behavior change. The Internet intervention will utilize an intuitive and engaging interface that will provide the look, feel, and navigation similar to that of an application or "app" that one might use on a tablet (e.g., iPad) or smartphone, rather than a traditional website.

The ITW will utilize a computerized tailoring algorithm to provide specific messages and content to each participant based on his/her beliefs and behaviors. Sections of the website include: Introduction – purpose, outline of content, features, instructions, and frequently asked questions, overview of melanoma information and risk factors etc.; Getting Ready to Do a Skin Self Check – includes sections on when and how to do a thorough SSE, asking for assistance, what to look for, overcoming barriers, gaining confidence, what to do if you see something suspicious; Monthly Skin Self-Check – guides the user through conducting a SSE and recording moles on a body mole map; Practice Sun-Safe Behaviors – overview of sun-safe behaviors, risks of tanning, overcoming barriers, sun-safety during outdoor activities, gaining confidence:

Protocol Version Date: 4/5/22

Sun-Safe Action Plan – allows the user to create and review an action plan for engaging in sun-safe behaviors and avoiding risky UV behaviors (e.g., sunbathing, indoor tanning).

Up to 30 melanoma patients will provide input and feedback on an iterative basis throughout the development and usability testing process. After providing informed consent, participants will complete a brief survey (in person at Rutgers CINJ/RWJMS, via telephone, secure website) described in Section 4.1. In order to minimize participant burden, we will use multiple, flexible methods for obtaining input and feedback from patients (e.g., telephone, in-person interviews, and focus groups). Draft website content materials will be presented to participants in a semi-structured format and their feedback will be elicited. Initially, design and learning activities for the ITW will be evaluated by participants using paper prototypes. Subsequent prototypes will be web-based. Participants will be reimbursed for their valued time and participation with gift cards (at a rate of \$25 per hour up to a maximum of 5 hours).

We expect that Phase 1 of the project will yield a set of understandable, acceptable, and appealing web features that are customized to the needs, capabilities, and preferences of melanoma patients.

3.2. Phase 2: RCT of the Efficacy of the Intervention

Consented patients will be provided with a link to a secure, password-protected website to complete a baseline survey. After completing the survey online, patients will automatically be randomized to the ITW or Usual Care condition. Patients will be stratified according to disease stage and time since diagnosis (3–<14 months vs. 14–24 months) and then, within strata, block randomized using blocks of four or six patients. The study biostatistician, [name], was responsible for creating the randomization schedule and overseeing the randomization process, following standard operating procedures of the Rutgers CINJ Biometrics Shared Resource. After 8 weeks, study participants will be prompted (via email, as well as by telephone, text message [with their permission] and mail, as necessary) to complete an online survey (follow-up 1), followed by additional online surveys 24 weeks (follow-up 2) and 48 weeks post-baseline (follow-up 3). The estimated time to complete each online survey varies from 40 minutes for the baseline to 20 minutes for the follow-up 3 survey.

Participants randomized to the ITW condition will be provided with a link to the intervention website, which they will be free to access any time throughout their study participation. To promote usage of the website, the modules of the ITW will be available to participants on a staggered basis using event- and time-based triggers. Specifically, an initial set of modules will be available to participants immediately. Once those modules have been completed (which we anticipate will take participants no longer than 2 weeks), a final module will be introduced after one week. This approach of introducing website intervention content in a staggered manner has been shown to facilitate greater use of, and exposure to, health promotion websites (Brouwer et al., 2011). We anticipate that each module will take from 30–40 minutes to complete, although participants will be encouraged to review each module regularly. Key elements of the ITW will be available (for example, as fully formatted .pdf documents) for participants to download and print.

Participants randomized to the Usual Care condition will receive no additional intervention aside from their usual non-study care. At the end of their participation in the study, participants in the Usual Care group will be offered the ITW intervention.

All participants will receive a \$25 gift card for completing each survey.

3.3 Phase 3: Qualitative Interviews:

Protocol Version Date: 4/5/22

Up to 50 study participants who have completed at least the How to Use Tutorial of the ITW will be randomly selected to participate in a qualitative interview lasting up to 45 minutes (for which they will receive a \$25 gift card). The interviews will consist of a semi-structured discussion to explore the participants' thoughts and experiences with regard to the ITW.

All of the telephone interviews will be digitally recorded and subsequently transcribed, which will allow them to be reviewed by the full research team. In line with our prior research studies, the telephone interviews will be transcribed under a fee-for-service agreement by trained personnel at the University of Pittsburgh Qualitative Data Analysis Program (QDAP). The interview recordings will be sent to the QDAP using a secure Internet file transfer protocol (FTP). After the transcription and translation has been completed for each interview, the QDAP will delete the respective recording. If any names or other potentially identifying information are mentioned during the interview, the relevant information will be removed from the audio recording prior to transcription. The research team will meet regularly to discuss the interview transcripts and to refine survey items, as necessary. We have used a similar approach in several prior skin cancer-related studies, and the qualitative interviews provided a rich source of relevant information that directly informed subsequent studies that have been conducted.

3.4. Duration of Study

Phase 1 of the project will last approximately 18 months. In Phase 2 of the project, participants will take part in the study for 12 months. Phase 3 of the project will last for approximately 6 months.

3.5. Study Sites

Recruitment of participants and human subjects interactions will take place at Rutgers, The State University of New Jersey, Saint Barnabas Medical Center (see IRB approval letter for Saint Barnabas Medical Center), and the New Jersey State Cancer Registry. The online survey and the Internet intervention will be developed, hosted, and maintained at the University of Virginia (site PI: [name]). The role of the research team at the University of Virginia includes providing input, feedback, and advice concerning web program creation and implementation, and study design and recruitment procedures, as well as full survey and web intervention development, hosting, and maintenance. Specifically, the team at the University of Virginia will work to create the intervention and help to identify and determine the structural and functional features of the web program. In Phase 1 of the project, [name] and his team will consult with the study team at Rutgers University regarding intervention design and content, create functional documentation for the intervention, provide design services for the intervention website, implement the study team's content into the technology framework, complete programming of the client side of the intervention, and integrate and optimize the backend database needed to employ the randomized controlled trial, which will be implemented in Phase 2 of the project. Continued support and maintenance of the intervention will be provided throughout Phase 2. At the end of the randomized controlled trial, the team at the University of Virginia will retrieve and clean all of the data captured by the Internet intervention for analysis. The research team at the University of Virginia will have access to protected health information of recruited patients. Specifically, the eligibility criteria require that patients have a personal history of melanoma; additionally, the University of Virginia research team will know the name and email address of recruited participants, as this information is needed to send out automated emails as part of the study protocol.

3.6. Sample Size

Up to 30 individuals will take part in Phase 1 of the project. For Phase 2 of the project, we will recruit 420 participants. For Phase 3 of the project, we will recruit up to 50 participants. For the Phase 2 RCT study,

we conducted power calculations for the primary and secondary aims. (We did not conduct power calculations for Aim 3 because it is an exploratory aim.) For the primary aim (intervention efficacy), there are two primary outcomes: engagement in thorough SSE (binary outcome) and sun protection behavior index (continuous score) at 24 weeks post-baseline. At baseline, we anticipate that 9% of participants will be adherent to thorough SSE. Based on our own and others' prior research (Glanz et al., 2010; Janda et al., 2011; Manne et al., 2010; Weinstock et al., 2007), we anticipate that the rate of adherence to thorough SSE at 24 weeks post-baseline will be ≥35% in the ITW group and this will be at least 15 percentage points higher than the adherence rate in the Usual Care group. An increase in SSE of this magnitude would be considered a successful rate. We assume proportions of individuals completing SSEs are compared between treatments using a z-test. Allowing for 10% dropout at 24 weeks (a rate comparable to that experienced in our prior research; Manne et al., 2010) and an adherence rate to thorough SSE of up to 20% in the Usual Care group at 24 weeks post-baseline (which is at the upper end of what might be expected), 153 individuals would need to be recruited in each group to obtain 80% power. Power calculations for the sun protection behaviors outcome are based on results of prior tailored interventions, including our own (Glanz et al., 2010; Manne et al., 2010). In our prior RCT, sun protection scores at baseline were 2.8 for both groups and increased to 3.2 and 3.4 for the generic and tailored interventions, respectively. Given that the Usual Care control group in the current RCT is not an active control (the generic intervention in the prior study was an active control), we assume that the sun protection scores in that group would increase to a maximum of 3.0. Standard deviations were, on average, 0.66 at baseline and 0.76 at follow-up. We assume a correlation between baseline and follow-up measures of 0.60. Under these assumptions, recruiting 153 individuals to each group would provide more than 80% power to detect differences in changes in sun protection scores from baseline to 24 weeks post-baseline. For the secondary aim (intervention mediators), we utilized sample size tables for mediated effects based on simulation studies that model the two pieces of the mediating path (from intervention group assignment to mediating variable and from mediating variable to outcome) (Fritz & Mackinnon, 2007). Based on the results of relevant prior research, we conservatively assume that one of the two paths will have a regression coefficient of at least .14 (a small effect, according to Cohen's [1998] criteria) and the other will have a regression coefficient of at least .26 (a small-to-moderate effect). Under those assumptions, and allowing for 10% dropout at 24 weeks, recruiting 210 individuals to each group would provide 80% power to detect mediational effects (Fritz & Mackinnon, 2007). Overall, based on a consideration of the aforementioned factors, we will recruit 210 individuals to each of the ITW and Usual Care groups, for a total sample size of N = 420, which will provide at least 80% power for the primary and secondary aims. We anticipate that at least 378 of the 420 patients (i.e., 90%) will complete the 24 weeks post-baseline assessment and 357 (85%) will complete the 48 weeks post-baseline assessment.

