5.1. Primary Aim

Aim 1. To evaluate the impact of the ITW versus Usual Care on SSE and sun protection behaviors among individuals diagnosed with melanoma. Hypothesis. Individuals assigned to the ITW will be more likely to engage in SSE and sun protection behaviors than those assigned to Usual Care.

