Using intent-to-treat analyses, we will compare engagement in thorough SSE and the sun protection behavior index for individuals in the ITW versus Usual Care, with the outcomes at 24 weeks as the primary focus. To handle missing data due to participant dropout, weighted generalized estimating equations (Little & Rubin, 2002; Preisser et al., 2002; Robins et al., 1995), with a logit link for SSE (a binary variable) and an identity link for the sun protection behavior index, will be used to estimate the treatment effect with weights proportional to the inverse of the estimated probability of dropout. Score tests and estimates of regression coefficients for the treatment indicator variable will assess the effect of the intervention. Sensitivity analyses will examine the effect of intervention at follow-up controlling for any demographic information that differs significantly by intervention group at baseline. These analyses are appropriate under the assumption that dropout is missing at random (MAR). Secondary analyses will use multiple imputation to examine the estimated treatment effect under different scenarios assuming the dropout is missing not at random (MNAR). In particular, for the sun protection behavior index, the mean for treated dropouts will be assumed equal to the estimated mean for Usual Care non-dropouts plus a sensitivity parameter, set at values of 25%, 50%, 75% and 100% of the estimated treatment effect (representing scenarios ranging from dropouts experiencing almost all to none of the estimated treatment effect). These analyses provide a picture of potential bias due to informative dropout (Little, 1994; Minini & Chavance, 2004a, 2004b; National Research Council, 2010). Additional multilevel models (Raudenbush, 2003) will examine the effect of the intervention on changes in thorough SSE and sun protection behaviors over time, comparing changes across 8, 24 and 48 weeks. Specifically, generalized estimating equations will be used for estimation and testing (Liang & Zeger, 1986; Ukoumunne & Thompson, 2001). Additional analyses will focus on the effect of the intervention on the number of SSEs performed, the number of body areas examined, and the individual sun protection behaviors (wearing sunscreen with an SPF \geq 30, wearing a long-sleeved shirt, wearing a wide-brimmed hat, and staying in the shade). Analyses will also focus on the effect of the intervention on use of sunglasses, wearing long pants, spending time in the sun in order to get a tan, and the number of sunburns.

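### Aim 1 has two separately tested primary outcomes but no stated alpha, success rule or multiplicity control; if a win on either may support the aim, false claims of benefit are about 4.0-4.9% against 2.5%

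*Combined protocol and SAP*

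**What the plan says.** Section 3.6 (Sample Size) states that for the primary aim "there are two primary outcomes: engagement in thorough SSE (binary outcome) and sun protection behavior index (continuous score) at 24 weeks post-baseline". It powers the two outcomes one at a time. For SSE it assumes 35% against 20% and 10% dropout, and concludes that "153 individuals would need to be recruited in each group to obtain 80% power". For the sun protection index it reports that the same 153 gives more than 80% power. The section ends with 210 per group, "which will provide at least 80% power for the primary and secondary aims". It gives no alpha, no sidedness and no joint power.

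Section 5.1 (Primary Aim) fits a weighted GEE to each outcome, "with a logit link for SSE (a binary variable) and an identity link for the sun protection behavior index", and adds: "Score tests and estimates of regression coefficients for the treatment indicator variable will assess the effect of the intervention". It sets no significance threshold and does not say how two results become one conclusion.

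Three passages come near a rule without giving one:
- In 3.6, after the 15-point SSE difference: "An increase in SSE of this magnitude would be considered a successful rate". This describes an effect size for SSE only.
- The Aim 1 hypothesis in 5.1: "Individuals assigned to the ITW will be more likely to engage in SSE and sun protection behaviors than those assigned to Usual Care". The conjunction could mean that both are required, but no test rule follows from it.
- Section 5.3 (Exploratory Aim) applies a Hochberg procedure, but only to the candidate moderators of Aim 3.

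**The concern.** One efficacy aim rests on two tests. If one outcome is significant and the other is not, the plan does not say whether Aim 1 is met, and the rule could be chosen after the results are known. A split result is plausible. The outcomes are different behaviours, and the Phase 2 eligibility criteria in 3.7 admit people who are non-adherent on either one, so some participants may have little room to improve on the other.

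The consequences differ by rule. If either outcome suffices, two unadjusted tests give two chances of a false claim of benefit. If both are required, the error rate is not inflated, but the power that matters is the joint power, which is not reported. If each behaviour is a separate claim, nothing limits the error across the pair.

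**Working it through.** **Inputs from 3.6.** SSE 35% (ITW) and 20% (Usual Care); 80% power; 10% dropout; 378 of 420 completing 24 weeks, so 189 per arm. For the sun index: "Standard deviations were, on average, 0.66 at baseline and 0.76 at follow-up", with a baseline to follow-up correlation of 0.60.

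**Assumptions.** (a) Two-sided 0.05 per outcome, inferred in step 1. (b) A sun index difference of 0.4: the prior trial's tailored arm reached 3.4, and Usual Care here is put at a maximum of 3.0, but no ITW value for this trial is stated. (c) The correlation between the two test statistics, which the plan does not give. (d) z-tests on completers as an approximation to the weighted GEE.

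**1. Reproducing the 153.** Pooled two-proportion z-test, mean rate 0.275:

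n = [z(1-α/2) × √(2 × 0.275 × 0.725) + 0.842 × √(0.35 × 0.65 + 0.20 × 0.80)]² / 0.15²

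| Two-sided α | Completers per arm | Recruited (/0.9) |
|---|---|---|
| 0.05 | 137.9 | 153.2 |
| 0.025 | 167.1 | 185.7 |

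The stated 153 fits one unadjusted test at two-sided 0.05. One-sided 0.05 gives 122 and the continuity-corrected two-sided version 168, so neither fits.

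**2. Limit on the correlation.** With no treatment effect, the two test statistics correlate about as the two outcomes do within a person. A binary outcome with rate p and a normal index cannot correlate above φ(z_p)/√(p(1-p)). At p = 0.20 this is 0.280/0.400 = 0.70; at p = 0.35 it is 0.370/0.477 = 0.78. The range examined is therefore 0 to 0.78.

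**3. Error if either outcome may win and neither effect is real.** False claim of benefit = 1 - Φ₂(1.96, 1.96; ρ). At ρ = 0 this is 1 - 0.975² = 4.94%. In either direction at ρ = 0 it is 1 - 0.95² = 9.75%.

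| ρ | False benefit (one test: 2.5%) | Either direction (one test: 5%) |
|---|---|---|
| 0 | 4.9% | 9.75% |
| 0.2 | 4.8% | 9.6% |
| 0.5 | 4.5% | 9.1% |
| 0.7 | 4.2% | 8.3% |
| 0.78 | 4.0% | 7.9% |

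With Holm (simulation, 2,000,000 draws per correlation), false benefit is about 2.5% at ρ = 0 and 2.1% at 0.7; in either direction it is 4.9% and 4.3%.

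**4. Error if both are required.** With no effect on either outcome, the false-claim rate is 0.025² = 0.06% at ρ = 0 and 0.05 - 0.0396 = 1.0% at ρ = 0.78. If only one effect is absent it is at most 2.5%. There is no inflation.

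**5. Power at 189 completers per arm.**
- SSE: 90.7% at 0.05 and 85.1% at 0.025.
- Sun index: the SD of change is √(0.66² + 0.76² - 2 × 0.6 × 0.66 × 0.76) = 0.641. Section 3.6 powers differences in change, while 5.1 compares 24-week values, so both 0.641 and the follow-up SD of 0.76 are shown. Power = Φ(d/(SD × √(2/189)) - 1.96). Joint power is this times 0.907, assuming independence.

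| Difference d | Sun index power at 0.05 (SD 0.641 / 0.76) | Joint power |
|---|---|---|
| 0.4 | >99.9% / 99.9% | about 91% / 91% |
| 0.3 | 99.5% / 97.0% | 90% / 88% |
| 0.2 | 85.8% / 72.5% | 78% / 66% |

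For d = 0.4 at two-sided 0.025, sun index power is 99.99% (SD 0.641) or 99.8% (SD 0.76).

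**The case against.** The strongest reply is that the inflation is conditional and that the text leans the other way. The hypothesis joins the two behaviours with a conjunction, and a both-required rule has no inflation. That stands as a limit on the concern: a reader might infer that the trial's error rate is inflated outright, and the documents do not support that, because they never say that either outcome suffices. Nor do they support the opposite inference, that the conjunction fixes a both-required rule. Section 3.6 powers each outcome separately and reports no joint power, so that reading is not carried through.

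A second reply is that these are two distinct behaviours with separate website sections, power calculations and models, so each may be its own claim. This reading is also open. Each claim would then keep its 2.5% error towards benefit, and whether to control error across the pair is partly a matter of judgement. But the plan lists both as primary outcomes under one aim and one hypothesis, so it should say if this is what it means.

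A third reply is that the practical consequence is small, since the mediation analysis sets N at 210 per group, which already exceeds the 185.7 needed for SSE at 0.025. That is correct, and it means that a reader should not conclude that the trial is too small for an adjusted SSE test. It does not supply the missing rule.

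**Conclusion.** The concern holds in this form: the plan runs two unadjusted primary tests and has no rule for a split result. That gap does not depend on any assumption. The error inflation is conditional. If a win on either outcome may support Aim 1 and neither effect is real, false claims of benefit are about 4.0-4.9% against 2.5%, and errors in either direction about 7.9-9.75% against 5%. These figures rest on the inferred two-sided 0.05, on test correlations between 0 and about 0.78, and on a roughly normal index. A lower figure such as 3.5% would need a correlation near 0.9, beyond what these two outcomes can reach.

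A reader might also take about 91% as the joint power under a both-required rule. That holds only if the assumed 0.4 difference is right. At 0.2, which was the gap between the tailored and generic arms (3.4 and 3.2) in the prior trial with an active control, joint power is 66-78%, below the promised 80%.

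This should be corrected. It is a missing rule that wording can repair, not a flaw in the design.

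**What to change.** In 5.1, state the success rule before the data are analysed. The choice belongs to the sponsor.
- If either outcome can support a claim: *The two primary outcomes at 24 weeks will be tested with Holm's procedure at an overall two-sided 5% level; efficacy will be claimed only for the outcome(s) significant under this procedure in favour of ITW.*
- If both are required: *Each primary outcome will be tested at two-sided 5%; Aim 1 is met only if both are significant in favour of ITW.* Joint power should then be reported.

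Holm is suggested because it needs no assumption about the correlation between the tests. The direction must be stated, since a two-sided result favouring Usual Care should not support the aim.

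In 3.6, state two-sided 5% and say that 153 per group is for a single unadjusted SSE test. Add that at 189 completers per arm SSE power is about 91% at 0.05 and about 85% at 0.025 (z-test approximation). Label the 0.4 sun index difference as assumed, with its source, and give joint power over a range: about 91% at 0.4, 88-90% at 0.3 and 66-78% at 0.2 (SD 0.76 to 0.641, independence assumed).

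Cost: wording only, with N unchanged at 420. Under Holm, SSE power falls to about 85% only when the sun index is not significant; with a true index difference of 0.4 it stays at about 91%. Under a both-required rule, a win on one outcome alone would not meet Aim 1.
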